Rationale: Given that in persons post-stroke, improving walking is 1) independently related to overall health status; 2) a strong predictor of functional recovery and 3) the most often stated goal during rehabilitation, interventions aimed at improving functional walking status are critical to increasing independence and improving quality of life for patients and their caregivers. The advanced methodologies proposed herein and the novel theoretical framework we have developed allow for detailed investigation of the neural and muscular factors that contribute to (changes in) muscle power generation. In addition, the state-of-the-art assessments of walking provide a comprehensive evaluation of locomotor behavior and the biomechanical mechanisms underlying hemiparetic walking performance. Moreover, we seek to identify the muscular characteristic(s) that best predict functional improvement and provide evidence establishing the characteristics of those most likely to benefit (or not) from training.

Summary of Experiment & Research Design: We will determine the relationship between changes in neural and muscular factors and improved power generation following training. We will also assess functional improvements via the proposed clinical assessments as well as through full biomechanical evaluations of walking.

Data Analysis Plan: We will assess relationships for changes in central activation, muscle CSA and [Pi] (predictor variables) with improvements in muscle power generation (criterion variable) and self-selected walking speed by using mixed effects regression models, which, by incorporating random subject effects, will allow us to account for correlation of measures made on the same individual over time. We will also use measures of muscle power generation in the paretic and non-paretic knee extensor and plantar flexor muscle groups as predictor variables in a multivariable linear regression model to assess relationships with self-selected walking speed. Standardized β coefficients from these regression models will help us determine which factors have the strongest influence on our outcome variables (i.e. power generation and self-selected gait speed).

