Secondary Questions: Although this proposal is not powered to examine differences in efficacy and mechanisms of response between POWER training and other intervention approaches (e.g., locomotor training), we intend to investigate these via exploratory post-hoc analyses to compare with an existing data set from a Locomotor Training trial in persons with chronic stroke (the same population we will be studying) recently completed by us (VA Merit Award B3983, [name] PI). We will first compare the effect on self-selected and fastest comfortable walking speed for the two

interventions. Then we will conduct a detailed biomechanical assessment, from which we will calculate moments, powers, work, and kinematics, as well as the electromyography (EMG) data to measure muscle coordination. Although we do not present specific hypotheses related to differences between POWER training and the task-specific approach utilized in our previous trial, we believe this information will be extremely valuable in explaining the neural coordination associated with recovery of walking and provide insight on the emerging similarities and differences of these presumably distinct approaches to locomotor recovery. [name] has a proven track record of performing successful quantitative analyses from biomechanical assessments and will direct the interpretation of these data. In addition, this proposal will leverage [name] currently funded R-01, which has already developed the tools to analyze the coordination of EMG activity during multiple locomotor tasks in even greater detail.

Expectation: We hypothesize that this type of training delivered separately to the paretic and non-paretic legs will result in improved functional performance that is associated with increased lower extremity muscle power generation (primarily the paretic plantar flexors). Further, we expect that post-hoc analyses of the characteristics of responders versus non-responders will be especially informative and will open the door for subsequent studies to study different adjunctive approaches to locomotor recovery.

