Sample size determination and Statistical Approach: A total of 28 subjects will be recruited for this study. With baseline data from n=28 subjects, we will have at least 80% power to detect measures of association (i.e. partial correlations) as small as 0.5 between neural/muscular adaptations and peak power generation. Our preliminary data suggest that the intraclass correlation between measures of power on paretic and non-paretic legs is extremely high (i.e. Spearman rho = 0.81, intraclass correlation coefficient [ICC - from mixed model] ~100%). This power estimate for Aim 1 is based on 1 observation per subject; although our mixed model approach for analyses for Aim 1 will include 2 observations per subject (i.e. paretic and non-paretic leg), the detectable correlation may not be substantially lower due to the strong intraclass correlation. For Aims 2 and 3, analyses rely on longitudinal measures, and we assume (based on experience with our patient population) that no more than 15% will fail to complete all assessments. With 28 subjects enrolled and a 15% attrition rate over time (resulting in complete data on 24 subjects), we would have at least 80% power to detect changes in measures from baseline to the end of the study equivalent to 0.6 standard deviation units (i.e. effect sizes). This power estimate is based on a paired t-test framework (i.e. pre-post comparisons), and thus power is likely underestimated, since our models will also include data from mid-intervention and follow-up time periods. For example, assuming an ICC of 90% associated with within-subject responses over 4 time periods, the effective sample size (see Campbell et al., 2001) would be slightly higher (~n=26), as would be our power (~83%) to detect an effect size of 0.6. Treatment effect sizes of 0.6 are consistent with our preliminary data, in which effect sizes of 0.7 (95% CI 0.5 to 0.9), 1.5 (95% CI 1.1 to 1.9, and 0.5 (95% CI 0.1 to 1.0) were observed for improvement in gait speed, paretic leg power, and non-paretic power, respectively. With complete data on 24 subjects, we will also be able to detect whether as little as 40% of the variability in changes in gait speed can be explained by changes in the neural / muscular adaptation measures, assuming an ICC of 90% associated with within-subject responses over 4 time periods. All power estimates assume 2-sided hypothesis tests and an alpha level of 0.05 and were conducted by a biostatistician using PASS 2008 (NCSS, Kaysville, Utah).

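### No written model relates walking gain to pre-training characteristics; the one comparison named for who benefits is a post-hoc responder contrast with no cut-off, and splitting about 24 completers would lose substantial power

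*Combined protocol and SAP*

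**What the plan says.** The opening statement of aims, the Aim 3 Rationale and the Aim 3 Innovation paragraph all make identifying who benefits a purpose of the study. The Rationale undertakes to "provide evidence establishing the characteristics of those most likely to benefit (or not) from training".

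Three places bear on how this would be done:

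- **Aim 3, Expectation.** "post-hoc analyses of the characteristics of responders versus non-responders will be especially informative". No responder definition, cut-off, list of characteristics, test or power is given. The Innovation paragraph refers again to post-hoc analyses for this purpose, without a method.
- **Aim 3, Data Analysis Plan.** Mixed models relate changes in central activation, CSA and [Pi] to improvement in muscle power and to self-selected walking speed. A multivariable linear regression relates walking speed to muscle power of the knee extensors and plantar flexors.
- **Procedures (Specific), Subject screening and clinical assessments.** Passive range of motion, spasticity and sensation are recorded so that their influence on training response can be examined retrospectively. No method is stated.

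The section on sample size determination gives a detectable effect for the continuous analysis: "as little as 40% of the variability in changes in gait speed can be explained by changes in the neural / muscular adaptation measures", with 24 completers. It gives none for a responder comparison.

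**The concern.** Someone deciding whom to train needs predictors that are known before training starts. A change in central activation during training is known only afterwards. It can explain a gain but cannot select patients. Aim 1 relates baseline measures to baseline power, and Aim 2 uses time as its key predictor, so neither fills the gap.

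That leaves the responder contrast as the only named comparison. Dividing a continuous gain into two groups discards information, which matters with about 24 patients. An unspecified cut-off also leaves room for results that depend on where the line is drawn. The risk is that real baseline predictors are missed, or that predictors tied to one cut-off are reported.

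**Working it through.** **Inputs from the documents** (Sample size determination and Statistical Approach, unless stated)

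- Tests: "All power estimates assume 2-sided hypothesis tests and an alpha level of 0.05".
- Completers: 28 × (1 − 0.15) = 23.8, taken as 24.
- Stated power: "at least 80% power to detect changes in measures from baseline to the end of the study equivalent to 0.6 standard deviation units", from a paired t-test. With four time points and an ICC of 0.90, the plan gives an effective n of about 26 and power of about 83%.
- Correlation of plantar-flexor power with self-selected speed (Preliminary Studies): 0.78 paretic, 0.46 non-paretic.

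**Not in the documents, so assumed:** a responder share of 50%, 33% or 25% (12, 8 or 6 of 24); a true correlation r between characteristic and gain; bivariate normality; a two-sample t-test after the split.

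**Step 1: the plan's own figures**

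- Paired t, n = 24: noncentrality 0.6 × √24 = 2.94 on 23 df gives 80.4%.
- Effective n = 24 × 4 / (1 + 3 × 0.90) = 96 / 3.7 = 25.9. At n = 26, power is 83.6%.
- R² = 0.40, n = 24: λ = 24 × 0.40 / 0.60 = 16. Power is 87% with three predictors and 82% with four.

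The first two reproduce. The R² figure is consistent with 80% power for up to four predictors.

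**Step 2: information kept after a split**

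For responder share p, the correlation shrinks by φ(z_p) / √(p(1 − p)). The square of this factor is the share of information kept.

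- p = 0.50: 0.3989 / 0.5000 = 0.798; squared 0.637; 24 × 0.637 = 15.3
- p = 0.33: 0.3636 / 0.4714 = 0.771; squared 0.595; 24 × 0.595 = 14.3
- p = 0.25: 0.3178 / 0.4330 = 0.734; squared 0.539; 24 × 0.539 = 12.9

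So 24 patients count as roughly 13 to 15.

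**Step 3: power at n = 24, two-sided 0.05** (100,000 simulated trials per row; correlation test on continuous gain versus t-test of the characteristic between groups)

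| True r | Continuous | 12 responders | 8 responders | 6 responders |
|---|---|---|---|---|
| 0.40 | 51.0% | 33.3% | 31.1% | 28.1% |
| 0.50 | 73.2% | 50.5% | 47.3% | 42.4% |
| 0.55 | 82.7% | 59.9% | 56.3% | 51.0% |
| 0.632 (R² = 0.40) | 93.7% | 75.6% | 71.9% | 65.9% |

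Letting the number of responders vary around the same share changes the split figures by about one point. The smallest r detectable with 80% power is about 0.54 with continuous gain and about 0.65 to 0.72 after a split.

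**Step 4: if the cut were chosen from the data**

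With no true association, taking the best of three cuts (33%, 50%, 67% responders) raises the false-positive rate for one characteristic from 5% to about 12%. With seven cuts between 25% and 67% it is about 18%.

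**Step 5: what the remedy delivers**

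The continuous column is for a simple correlation with gain. Adjusting for baseline speed changes it. Let b be the correlation of the characteristic with baseline speed, and assume gain does not depend on baseline speed given the characteristic. The partial correlation is then r√(1 − b²) / √(1 − r²b²). At r = 0.55:

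- b = 0.46: 0.55 × 0.888 / 0.967 = 0.505; simulated power about 72%
- b = 0.78: 0.55 × 0.626 / 0.903 = 0.381; simulated power about 45%

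Five independent characteristics, each tested at 0.05, give 1 − 0.95⁵ = 23% chance of at least one false positive.

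**The case against.** The strongest reply is that continuous change is already the plan's main approach. The Aim 3 models do not split anything, and the 40% figure refers to continuous change in gait speed. The responder contrast is one sentence, outside any data analysis plan, openly post-hoc and meant to prompt later studies. The retrospective look at range of motion, spasticity and sensation is a second route and mentions no split. The losses in Step 3 therefore belong to an analysis that the documents do not spell out.

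Much of this stands, and it rules out three stronger readings that a reader might infer:

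- *That Aim 3 as a whole rests on a responder split.* It does not. The mechanism question is analysed with continuous models.
- *That the split is the only route to the who-benefits question.* It is the only named comparison, but the screening section adds another route without a method.
- *That the investigators will pick a cut-off after seeing the data.* No text says so. Step 4 shows what an open cut-off permits, not what is planned.

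A further fair point is that the remedy has limits. For a characteristic as closely tied to baseline speed as paretic plantar-flexor power, the adjusted model at r = 0.55 has about 45% power, below the unadjusted median split (about 60%). At r = 0.40 both methods are weak.

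What the reply does not answer is that a model of change on change cannot identify patients in advance, and no model of gain on pre-training characteristics is written down.

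**Conclusion.** The point holds as a minor gap in the analysis plan. A stated purpose of the study has no specified analysis, and the only comparison named for it would, if carried out as a split of gain, keep about 54% to 64% of the information. At r between 0.50 and 0.55, that costs roughly 22 to 32 percentage points of power for a single predictor.

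The size depends on the assumed responder shares, correlations and normality. The number of co-activation patterns takes only the values one to four, so normality does not fit that characteristic. The direction of the loss was the same under every share tried.

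A reader might also conclude that keeping gain continuous would make the study adequately powered to find who benefits. The figures do not support that: 80% power needs a correlation of about 0.54 or more, before any adjustment or multiplicity. With no concurrent control, neither method separates response to training from improvement for other reasons.

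**What to change.** Add one paragraph to the Aim 3 Data Analysis Plan:

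- Regress continuous gain in self-selected speed, baseline to week 8, on one baseline characteristic at a time, from a short list fixed in advance. Candidates already measured include central activation, CSA, [Pi], plantar-flexor power and the number of co-activation patterns. Range of motion, spasticity and sensation could join the list, which would give them a stated method.
- Show each result with and without adjustment for baseline speed.
- Report the results as exploratory, with confidence intervals and the number of characteristics examined.
- Use responder groups for description only, with the cut-off set before the gains are examined.

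This needs no new data, visits or patients. The costs to acknowledge are that a slope is harder to communicate than a group comparison; that adjustment lowers power for characteristics strongly correlated with baseline speed; that several predictors raise the false-positive risk; and that, with one arm, the text should speak of who improved rather than who improved because of training.

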Inclusion criteria will be: 1) age 50-70, 2) stroke within the past 6 to 24 months, 3) residual paresis in the lower extremity (Fugl-Meyer LE motor score <34), 4) ability to walk without assistance and without an AFO on the treadmill \geq 30 seconds at speeds ranging from 0.3 - 0.8 m/s, and 5) provision of informed consent. In addition, all subjects who meet criteria for the training portion must complete an exercise tolerance test and be cleared for participation by the study cardiologist. **Exclusion criteria** will be: 1) Unable to ambulate at least 150 feet prior to stroke, or experienced intermittent claudication while walking; 2) rating on Modified Ashworth Scale ≥ 3 at the knee or ankle; 3) limited lower extremity range of motion of the knee (passive flexion ROM < 90); hip (inability to achieve neutral 0° hip extension); or ankle (inability to achieve 0° of active dorsiflexion); 4) history of congestive heart failure, unstable cardiac arrhythmias, hypertrophic

cardiomyopathy, severe aortic stenosis, angina or dyspnea at rest or during ADL's; 5) History of COPD or oxygen dependence; 6) Preexisting neurological disorders, dementia or previous stroke; 7) History of major head trauma; 8) Legal blindness or severe visual impairment; 9) history of significant psychiatric illness 10) Life expectancy <1 yr., 11) Severe arthritis or other problems that limit passive ROM; 12) post-stroke depression (PHQ-9 ≥ 10), 13) History of DVT or pulmonary embolism within 6 months; 14) Uncontrolled diabetes with recent diabetic coma, or frequent insulin reactions; 15) Severe hypertension with systolic >200 mmHg and diastolic >110 mmHg at rest; 16) Previous or current enrollment in a trial to enhance motor recovery; 17) Presence of non-MR compatible implants, pregnancy or severe claustrophobia.

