Subject monitoring during testing and training: Blood pressure (BP) and heart rate (HR) will be monitored prior to, during, and at completion of each session. Subjects' resting diastolic BP must be <100 mmHg, systolic < 200 mmHg, and heart rate <110 beats/min to begin the testing (Mahler et al, 1995, Rimmer et al, 2000). Criteria for termination include subject complaints of shortness of breath, light-headedness, confusion, severe headache, or dyspnea; onset of angina; excessive blood pressure (systolic BP > 200 mm Hg, diastolic BP >110 mm Hg), or drop in systolic BP >10 mm Hg and inappropriate bradycardia (drop in heart rate >15 bpm).

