Inclusion criteria will be: 1) age 50-70, 2) stroke within the past 6 to 24 months, 3) residual paresis in the lower extremity (Fugl-Meyer LE motor score <34), 4) ability to walk without assistance and without an AFO on the treadmill \geq 30 seconds at speeds ranging from 0.3 - 0.8 m/s, and 5) provision of informed consent. In addition, all subjects who meet criteria for the training portion must complete an exercise tolerance test and be cleared for participation by the study cardiologist. **Exclusion criteria** will be: 1) Unable to ambulate at least 150 feet prior to stroke, or experienced intermittent claudication while walking; 2) history of congestive heart failure, unstable cardiac arrhythmias, hypertrophic cardiomyopathy, severe aortic stenosis, angina or dyspnea at rest or during ADL's; 3) History of COPD or oxygen dependence; 4) Preexisting neurological disorders, dementia or previous stroke; 5) History of major head trauma; 6) Legal blindness or severe visual impairment; 7) history of significant psychiatric illness 8) Life expectancy <1 yr., 9) Severe arthritis or other problems that limit passive ROM; 10) post-stroke depression (PHQ-9 \geq 10), 11) History of DVT or pulmonary embolism within 6 months; 12) Uncontrolled diabetes with recent weight loss, diabetic coma, or frequent insulin reactions; 13) Severe hypertension with systolic $>$ 200 mmHg and diastolic $>$ 110 mmHg at rest; 14) Previous or current enrollment in a clinical trial to enhance motor recovery; 15) Presence of non-MR compatible implants, pregnancy or severe claustrophobia.

b. Sources of Materials: All data will be acquired for purposes of research only and will be kept confidential. Data will be coded and not traceable to individuals in any publication. Files will be stored in locked offices or password-protected servers dedicated to [name] and key study personnel only.

c. Potential Risks: The risks of the exercise tolerance tests are minimal but could include fainting, falling, irregular heartbeat, and very rarely heart attack, stroke, or death (less than 1 in 2500 cases). Professional staff (exercise physiologist, physical therapist, and cardiologists) will be present and available throughout and emergency treatment will be available if it becomes necessary.

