a. Recruitment and Informed Consent: A total of fifty-six subjects (male and female; n=28 post-stroke and n=28 controls), ages 50-70, will be screened and recruited for the proposed study. The pool of post-stroke candidates for the study will be recruited from the Ralph H. Johnson VAMC; the Medical University of South Carolina; and the Charleston, SC area communities. Before any tests are conducted, the protocol and tests to be used in this study and the potential risks and benefits of participation will be explained to each potential subject. All participants will review and sign an informed consent form approved by the local Institutional Review Board prior to initiating any portion of the study.

b. Protection Against Risk: A licensed physical therapist will be present during all treatment sessions. In addition, during all treadmill walking trials, a safety harness will be worn to provide assistance in the event of loss of balance. The research staff will closely monitor the subject to ensure their comfort. Any adverse events will be recorded and monitored as required by our Institutional Review Board. In the event of an adverse medical event, standard facility emergency procedures will be followed and proper personnel notified. The PI on this proposal and is a licensed physical therapist with several years of experience in the development and implementation of exercise interventions. Any adverse events will be recorded and monitored as required by the IRB. On-site medical services will be available in the event of adverse events to the subjects. Subjects will be able to terminate the training or testing sessions at their request at any time without prejudice. Minimization of risk will be accomplished by monitoring vital signs within prescribed criteria for termination of the training session. We will follow the American College of Sports Medicine criteria for terminating an inpatient exercise session which includes: subject complaints of light-headedness, confusion, or dyspnea; onset of angina; excessive blood pressure changes (systolic BP greater than 220 mmHg, diastolic BP greater than 110 mmHg); and inappropriate bradycardia (drop in heart rate >10 beats per minute).

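### The severe-hypertension exclusion requires both pressure limits to be exceeded, so one severely raised value does not exclude (minor safety-rule error)

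*Combined protocol and SAP*

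**What the plan says.** The eligibility list in Section D (Procedures (Specific), Subjects) gives exclusion 15 as "Severe hypertension with systolic >200 mmHg and diastolic >110 mmHg at rest". The list in Section E (Human Subjects Involvement and Characteristics) repeats it as exclusion 13, with the same limits and the same *and*.

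Four other places bear on blood pressure:

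- **Section D, Subject monitoring during testing and training, start limit:** "resting diastolic BP must be <100 mmHg, systolic < 200 mmHg", together with a heart-rate limit, before testing may begin. Pressure and heart rate "will be monitored prior to, during, and at completion of each session".
- **Same section, stop limit:** "systolic BP > 200 mm Hg, diastolic BP >110 mm Hg". The list also includes a heart-rate drop of more than 15 bpm.
- **Section D, Exercise Tolerance Testing:** resting pressure is recorded before exercise, but no resting limit is stated. The high-pressure stop during the test is 220/120 or above.
- **Section E, Protection Against Risk, stop limit:** "systolic BP greater than 220 mmHg, diastolic BP greater than 110 mmHg", with a heart-rate drop of more than 10 beats per minute.

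In addition, those who qualify for training "must complete an exercise tolerance test and be cleared for participation by the study cardiologist".

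**The concern.** An exclusion for severe hypertension would be expected to act when either pressure is severely raised. Joined by *and*, it acts only when both are. The protocol's other resting rule, the start limit in the monitoring section, requires each value to pass on its own. The entry rule therefore admits resting pressures at which the same protocol refuses to begin testing.

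The participants are stroke survivors who will perform a graded exercise test, maximal dynamometer contractions, maximum-velocity resistance exercise and jump training. At stake is whether the written entry screen does its job, or leaves the decision to later same-day checks and clinical judgement. Nothing statistical depends on it.

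**Working it through.** The plan gives no figure to reproduce, so the check is one of logic. Let S and D be resting systolic and diastolic pressure in mmHg.

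Rules, with their sources:

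- Exclusion as written (both eligibility lists): S > 200 and D > 110.
- Exclusion if reworded: S > 200 or D > 110.
- Start limit (Section D, monitoring): S < 200 and D < 100.
- Session stop, Section D: S > 200 or D > 110.
- Session stop, Section E: S > 220 or D > 110.
- Exercise-test stop (Section D): 220/120 or above.

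The two session stop lists separate their limits with a comma. I read that as *or*.

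| Resting S/D | Excluded as written? | Excluded with *or*? | May begin testing? | Above Section D stop? | Above Section E stop? | At exercise-test stop? |
|---|---|---|---|---|---|---|
| 215/105 | No (105 is not >110) | Yes | No | Yes | No | No |
| 190/115 | No (190 is not >200) | Yes | No (115 is not <100) | Yes | Yes | No |
| 210/115 | Yes | Yes | No | Yes | Yes | No |
| 190/95 | No | No | Yes | No | No | No |

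**Eligibility.** Two ranges are eligible although they lie above a Section D stop limit: S > 200 with D of 110 or below, and D > 110 with S of 200 or below. Every reading in either range fails the start limit, since S > 200 contradicts S < 200 and D > 110 contradicts D < 100. With *or*, the exclusion and the Section D stop limit become the same condition. Both ranges then close, and no reading below the stop limits is newly excluded.

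**Exercise test.** The start limit is a condition for beginning testing, under a heading that covers testing and training. It does not name the exercise tolerance test. That test has its own section, with no resting limit and a stop that neither 215/105 nor 190/115 reaches. Its text disapproves participation after a test stopped for electrocardiographic findings and states no such consequence for pressure. Whether the start limit governs the exercise test is therefore left open.

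**Session stop limits.** In whole units, the Section D and Section E lists disagree in two places:

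- Systolic 201 to 220 with diastolic 110 or below: Section D stops, Section E does not.
- A heart-rate drop of 11 to 15 bpm: Section E stops, Section D does not.

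Neither list is the stricter on both counts.

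**The case against.** The strongest reply is that the start limit already deals with these patients. It applies each limit separately and is stricter on diastolic pressure (100 against 110), and no reading in the two ranges passes it. Trainees also need a completed exercise test and a cardiologist's approval. Most of this stands, and it keeps the point minor. It does not make the correction redundant. The start limit is a same-day gate, so a patient can be enrolled and then turned away at each visit while the pressure stays raised. Clearance applies only to those entering training and has no stated pressure criterion.

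A second reply is that the fix is uneven: a patient with a resting diastolic of 105 would remain eligible and still could not start. That is true. The difference is that 110 is the protocol's own level for severe diastolic hypertension, and the fix enforces it without introducing a new threshold. Between 100 and 110, the protocol bars the patient on the day but does not call the value severe.

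A third reply is that the documents define severe hypertension only through the combined condition, so *and* might be deliberate. The text does not rule this out. But the same 200 and 110 reappear as session stop limits, and the start limit tests each value alone, so a deliberate joint requirement is unlikely.

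On the stop limits, staff who follow both lists can stop at whichever trigger comes first. A reader might infer that staff have no workable rule for systolic 201 to 220. That goes too far. The lists can be followed together, but the protocol does not say that they should be, or which one governs.

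**Conclusion.** The point holds as a minor safety-rule error. As written, one severely raised resting value does not exclude, in either list, and nowhere do the documents say that it should. The consequence is a gap in the entry rule that later checks largely cover.

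A reader might infer that patients with dangerous pressures would be tested or trained. The documents do not support that: the start limit bars every such reading where it applies, and a cardiologist must clear each trainee. The one uncertain step is the exercise tolerance test, where the text does not say whether the start limit applies.

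The number of patients affected cannot be estimated from the documents. The conclusion on eligibility needs only a literal reading of *and*. The comparison with the session stop limits also assumes that their commas mean *or*. The disagreement between the two session stop lists is real but separate, and adds no weight to the eligibility point. No endpoint, sample size or analysis is affected.

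**What to change.** 1. In both eligibility lists (Section D, exclusion 15; Section E, exclusion 13), replace *and* with *or*: resting systolic >200 mmHg or diastolic >110 mmHg.
2. State in the monitoring section, or under Exercise Tolerance Testing, that the resting start limit (systolic <200, diastolic <100) also applies before the exercise tolerance test. Leave the limit itself unchanged.
3. Replace the session stop limits in Sections D and E with one list that takes the stricter value of each: systolic >200 mmHg, diastolic >110 mmHg, heart-rate drop >10 bpm. State that any one is enough to stop. Carry over triggers that appear in only one list, such as the systolic drop in Section D.
4. Keep 220/120 as the stop limit for the graded exercise test only, and say so.

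The cost is one word in each eligibility list, one sentence on the exercise test and one shared stop list. In practice there may be a few more screen failures or stopped sessions.
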